### **5.9.1 Emergency Unblinding**

Treatment assignment should remain blinded unless the knowledge is necessary to determine emergency medical care, as determined by the Investigator. Emergency unblinding will be done using the study IWRS system in consultation with the Medical Monitor and the Sponsor. Blinding of study treatment is critical to the integrity of this clinical trial and therefore, if a subject's treatment assignment is disclosed to the Investigator, the subject will have the IP discontinued.

## **6 DATA ANALYSIS**

Data will be handled and processed according to the Contract Research Organization's Standard Operating Procedures, which are written based on the principles of GCP.

### **6.1 Statistical Methods**

The methodology presented below is a summary of the more detailed analysis plan that will be presented in the Statistical Analysis Plan (SAP). The SAP will be finalized before the database is locked and unblinded. Any changes to the methods described in the final SAP will be described and justified in the clinical study report.

All statistical processing will be performed using SAS® (Version 9.4) unless otherwise stated. No interim efficacy analyses are planned.

Descriptive statistics will be used to provide an overview of the efficacy, safety and pharmacokinetic results. For categorical parameters, the number and percentage of subjects in each category will be presented. The denominator for percentage will be based on the number of subjects appropriate for the purpose of analysis. For continuous parameters, descriptive statistics

will include n (number of subjects), mean, standard deviation (SD), median, minimum, and maximum.

### **6.1.1 Determination of Sample Size**

There are approximately 300 subjects planned for this study. Approximately 200 subjects will receive ARQ-154 foam 0.3% QD; approximately 100 subjects will receive vehicle foam QD.

The sample size was selected to provide an adequate number of subjects to compare the efficacy of ARQ-154 treatment to vehicle and to provide an adequate number of subjects needed for a safety database.

This sample size provides 96% power at the  $\alpha=0.05$  level to detect a 22.4% difference between treatment groups for S-IGA Success at Week 8 using a 2-sided Chi-squared test. The results from a recent phase 2b study (ARQ-151-201) of ARQ-151 compared to vehicle treatment were used to estimate the treatment difference and it is assumed that the S-IGA response in the present study are similar to IGA responses seen with ARQ-151. Specifically, in the phase 2b trial, 32.2% of subjects reported IGA success in the ARQ-151 0.3% group and 9.8% of subjects reported IGA success in the vehicle group.

The number of subjects to be enrolled will also provide sufficient power for most secondary endpoints.

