#### **4.3.1 Randomization**

Assignment of active drug or vehicle will be made at a 2:1 ratio according to a computer-generated randomization list, stratified by country, Baseline S-IGA (S-IGA=2 vs. S-IGA $\geq$ 3), and Baseline B-IGA (B-IGA=2 vs. B-IGA $\geq$ 3).

Randomization will take place at Baseline after the subject has been found to be fully eligible for participation. Kits containing IP will be assigned to each subject using an internet-based randomization system (IWRS). A subject may receive more than one kit for the treatment period. Subjects will be trained by the study site staff to apply ARQ-154 foam 0.3% QD or vehicle foam QD to lesions of scalp and body psoriasis up to a maximum application area of 25% BSA.

The kits and foam cans are blinded and each kit is numbered with a unique kit number.

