For this study, the primary estimand is the odds of achieving S-IGA success at 8 weeks; that is, the ratio of the odds of achieving S-IGA success at 8 weeks roflumilast foam 0.3% relative to the odds of success at 8 weeks of using a matching vehicle cream. In the course of the 8-week randomized treatment period, subjects may be exposed to possible known or unknown intercurrent events that could possibly impact the estimand, such as treatment discontinuation due to a specific adverse effect or perhaps a lack of effect. The “Treatment Policy Strategy” has been adopted for handling all known or unknown intercurrent events in this study. To this end, the ITT principle will serve as the analytical basis for interpreting the estimand. In other words, the odds ratio of achieving S-IGA success for roflumilast foam 0.3% relative to vehicle at 8 weeks will be evaluated regardless of the occurrence of any such intercurrent event. This estimand shall be estimated using the CMH approach. This approach produces an estimate that is the combined odds ratio resulting from adjusting for the possible effects of 3 classification factors: country, baseline S-IGA category (2 vs. ≥ 3) and baseline B-IGA category (2 vs. ≥ 3).

Categorical Data Analysis

The primary efficacy endpoint is success in S-IGA of disease severity, defined as an S-IGA of “Clear” or “Almost Clear” plus a 2-grade improvement from baseline at Week 8.

The primary endpoint will be analyzed using a CMH test stratified by country, baseline S-IGA category, and baseline B-IGA category. Statistical significance will be concluded at the 5% significance level (2-sided) or less, as discussed in Section 6.1.3. Odds ratios and 95% CIs for the odds ratios will be provided. Additionally, the 95% Wilson CIs for proportion of successes in each treatment group will be presented.

For the primary analysis, missing S-IGA scores will be imputed using multiple imputation as described in Section 6.1.4.1. These imputations will result in a minimum of 25 to a maximum of 250 complete analysis datasets, depending on the number of imputed monotone datasets required. The CMH analyses will be performed separately for each of the complete analysis data sets, and the results will be combined into one multiple imputation inference (estimated treatment effect and associated CI and *P* value). As a sensitivity analysis, the above described CMH test will be performed on the nonimputed data.

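### The stated 96% power does not follow from the stated inputs; 200 vs 100 subjects at 32.2% vs 9.8% gives about 99.7%

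*Protocol*

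**What the plan says.** Protocol 6.1.1 gives every input to a power calculation for two proportions:

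- Size and split: "There are approximately 300 subjects planned for this study", and "Approximately 200 subjects will receive ARQ-154 foam 0.3% QD; approximately 100 subjects will receive vehicle foam QD". Protocol 4.3.1 confirms the 2:1 allocation.
- Result claimed: "This sample size provides 96% power at the" 0.05 "level to detect a 22.4% difference between treatment groups for S-IGA Success at Week 8 using a 2-sided Chi-squared test".
- Source of the difference: "32.2% of subjects reported IGA success in the ARQ-151 0.3% group and 9.8% of subjects reported IGA success in the vehicle group". The section assumes that S-IGA response in this trial will resemble those rates.

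The Synopsis (Protocol 1.1) and SAP 3.2 repeat the same inputs and the same 96%. SAP 8.1.1 confirms the full alpha for the primary endpoint: "Statistical significance will be concluded at the 5% significance level (2-sided) or less". Protocol 6.1.3 plans no interim efficacy analysis. None of the three sample-size texts mentions attrition, a continuity correction or any other response rates.

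**The concern.** With 200 and 100 subjects, a 22.4-point difference starting from a vehicle rate near 10% is a large effect, and a 4% chance of missing it looks too high. If the result does not follow from the inputs, either the result is wrong or one of the rates, the allocation, the alpha or an attrition allowance is misreported, and the text does not show which.

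This sentence is the only quantified argument for 300 subjects. The same section also cites the safety database and adequate power for most secondary endpoints, but gives no numbers for either. The planning rates come from a different formulation (cream) and from IGA rather than S-IGA, so the useful information is how small a difference 300 subjects can detect. The text does not give that.

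**Working it through.** **Inputs** (Protocol 6.1.1): n1 = 200, n2 = 100, p1 = 0.322, p2 = 0.098, difference 0.224, two-sided alpha 0.05 (z = 1.960), chi-squared test.

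**Formula.** Power = Φ[(|p1 − p2| − z·SE0) / SE1]. SE0 uses the pooled rate, as the chi-squared test does, and SE1 uses the separate rates.

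1. Pooled rate = (200 × 0.322 + 100 × 0.098) / 300 = 74.2 / 300 = 0.2473.
2. SE0 = √[0.2473 × 0.7527 × (1/200 + 1/100)] = 0.0528.
3. SE1 = √[0.322 × 0.678/200 + 0.098 × 0.902/100] = √(0.001092 + 0.000884) = 0.0444.
4. (0.224 − 1.960 × 0.0528) / 0.0444 = 2.71, so power = Φ(2.71) = **99.66%**.

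Full enumeration of both binomial distributions with the Pearson chi-squared test also gives 99.66%. The plan's 96% is not reproduced.

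**Other ways of doing the calculation with the stated rates**

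| Variant | Power |
|---|---|
| Continuity-corrected | 99.45% |
| Fisher's exact test | 99.61% |
| Unpooled variance | 99.90% |
| Pooled variance under both hypotheses | 98.87% |
| One-sided alpha 0.05 | 99.90% |
| Two-sided alpha 0.025 | 99.12% |
| Allocation reversed (100 active, 200 vehicle) | 99.54% |
| Equal arms of 150 | 99.82% |

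None is within 2 points of 96%.

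**What would give about 96%** (main formula)

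- *Fewer subjects.* 132 + 66 = 198 gives 96.1%, a loss of 1 − 198/300 = 34%. Losses of 10%, 15% and 20% still leave 99.3%, 99.0% and 98.5%.
- *A smaller effect.* With 200:100 and vehicle at 9.8%, a 17.4-point difference gives 96.0%. A 15.0-point difference gives 89.9%.
- *A smaller alpha.* Two-sided 0.005 gives 95.6%.
- *Different base rates.* A 22.4-point difference at about 38.6% vs 61.0% gives 95.98%, the lowest power over all base rates.

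**Size of the gap.** 99.7% − 96% = 3.7 points. The type II error is 0.34% rather than 4%, a ratio of about 12.

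**The case against.** The strongest reply is that the power sentence names only a difference, and that the earlier trial is cited as the source of that difference. Power for a 22.4-point difference at 200:100 falls to a minimum of 95.98% over all base rates, which rounds to 96%. The figure may therefore be a deliberate worst-case-variance calculation, and replacing it with a value above 99% would discard that caution. Such a value would also suggest near-certainty for an unstratified test on borrowed rates, whereas the primary analysis is a stratified CMH test with multiple imputation.

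The worst case is a plausible origin, but no document mentions it. It also conflicts with the stated assumption that S-IGA responses will resemble 32.2% and 9.8%. It changes an input rather than being a variant of the stated calculation, so the text would still omit the assumption that produces its result.

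An attrition explanation is weaker. Combining the least favourable variance formula (pooled under both hypotheses) with 20% loss gives 96.65%, but neither choice is stated. The ITT analysis keeps all randomized subjects and imputes missing S-IGA scores (Protocol 6.1.2, SAP 6.1.4.1), so no third of the sample is dropped.

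Two parts of the objection stand. The error is conservative and affects no inference. And the calculation follows the plan's simple chi-squared test, so it does not describe the power of the CMH analysis.

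**Conclusion.** The 96% is wrong as written in Protocol 1.1, Protocol 6.1.1 and SAP 3.2. The stated inputs give 99.7%, and no standard form of the test at the stated sample size and rates brings it near 96%. This rests on taking the text literally: 200 and 100 analysed subjects, 32.2% and 9.8%, two-sided alpha 0.05 and an unstratified chi-squared test.

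The trial is not underpowered on its own assumptions. The consequence is that the efficacy target as printed does not explain 300 subjects, because 96% power would need about 198. The correction should be made, but it does not affect the validity of the primary analysis.

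**What to change.** In all three places, state that 200 and 100 subjects give more than 99% power for 32.2% vs 9.8% (two-sided chi-squared test, alpha 0.05).

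If 96% was intended to include an allowance, keep it and state the allowance. Examples are about 198 evaluable subjects, or the least favourable base rate for a 22.4-point difference.

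In either case add the smallest detectable difference with vehicle at 9.8%: about 17.4 points at 96% power and 15.0 points at 90%.

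The cost is one corrected sentence in three places, with no change to enrolment, endpoint or analysis.

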### **6.1.2 Subjects to Analyze**

Safety population will include all subjects who are enrolled and received at least one confirmed dose of IP. This population will be used for all safety analyses.

The Intention-to-Treat (ITT) population will include all randomized subjects. This population will be the primary analysis population for the analysis of efficacy endpoints.

Per-Protocol (PP) Population will include all subjects who are in the safety population, were at least 80% compliant with IP application, and showed no other serious deviations from the study protocol. This population will be used as a sensitivity analysis of primary and secondary efficacy endpoints.

The Pruritis population is a subset of the ITT population and includes subjects with Scalp Itch NRS score  $\geq 4$  at Baseline. This population will be used for the analysis of achievement of a 4-point reduction in Scalp Itch NRS pruritus score as compared to Baseline.

The PK population will include all subjects receiving the active drug with sufficient plasma concentrations of roflumilast to define a profile, as determined by the pharmacokineticist. This population will be used for analyses of PK parameters.

### **6.1.3 Interim Analysis**

No interim efficacy analyses are planned.

#### **6.1.4 Background and Demographic Characteristics**

Demographics, baseline disease characteristics, Baseline height, weight, and BSA will be summarized descriptively for all randomized subjects.

#### **6.1.5 Study Disposition**

Number of subjects randomized, receiving IP, completing study, and withdrawing prematurely (with reason for withdrawal) will be summarized by treatment group.

#### **6.1.6 Protocol Deviations and Eligibility Deviations**

The number of subjects with important protocol deviations and/or eligibility deviations will be summarized by category and by treatment group.

#### **6.1.7 Investigational Product Compliance**

The number of IP applications by each subject based on diary data will be summarized using descriptive statistics.

The amount of IP used by each subject based on can weight will be summarized by treatment using summary statistics (mean, SD, median, minimum, and maximum), and categorically.

IP compliance will be calculated based on number of applications divided by the expected number (amount) of IP for each subject. Compliance will be summarized descriptively by treatment group.

### **6.2 Study Objective**

#### **6.2.1 Primary Objective**

To assess the safety and efficacy of ARQ-154 foam 0.3% vs vehicle administered QD x 8 weeks in adolescents and adults with scalp and body plaque psoriasis.

### **6.3 Efficacy Evaluation**

#### **6.3.1 Primary Efficacy Endpoint**

The primary efficacy endpoint is S-IGA Success at Week 8, defined as achievement of an S-IGA score of 'Clear' or 'Almost Clear' plus a 2-grade improvement from Baseline.

The primary endpoint will be analyzed using a Cochran-Mantel-Haenszel test stratified by country, baseline S-IGA (2 vs.  $\geq 3$ ), and baseline B-IGA (2 vs.  $\geq 3$ ). Missing S-IGA and B-IGA scores will be imputed using multiple imputation. Sensitivity analyses of the primary endpoint may be conducted in by study site or groups of study sites.

### 6.3.2 Secondary Endpoints

The Secondary Efficacy Endpoints will include:

[figure not shown]
- B-IGA Success at Week 8, defined as achievement of Body-IGA (B-IGA) score of ‘Clear’ or ‘Almost Clear’ plus a 2-grade improvement from baseline
- PSSI-75 (subjects who achieve a 75% reduction in PSSI from Baseline) at Week 8
- For subjects with Baseline Scalp Itch NRS score  $\geq 4$ , achievement of  $\geq 4$ -point improvement from Baseline in Scalp Itch NRS at Week 8
- For subjects with Baseline Scalp Itch NRS score  $\geq 4$ , achievement of  $\geq 4$ -point improvement from Baseline in Scalp Itch NRS at Week 4
- For subjects with Baseline Scalp Itch NRS score  $\geq 4$ , achievement of  $\geq 4$ -point improvement from Baseline in Scalp Itch NRS at Week 2
- Time to PSSI-50
- Change from Baseline in total PSD score at Week 8
- Change from Baseline in total PSD score at Week 4
- PSSI-90 (subjects who achieve a 90% reduction in PSSI from Baseline) at Week 8

To control for multiple comparisons among the secondary endpoints, the following testing plan will be used:

Upon demonstration of statistical significance for S-IGA Success at Week 8, the secondary endpoint of B-IGA Success at Week 8 will be tested hierarchically at the 5% significance level.

If the test for B-IGA Success at Week 8 is significant, the  $\alpha$  of 0.05 will be split to test 2 families of secondary endpoints. The first family will be comprised of the PSSI-75, which will be tested at the  $\alpha = 0.03$  level. If the test of PSSI-75 is statistically significant, then  $\alpha = 0.03$  will be used with a Holm testing procedure to test the 4 endpoints of time to success in PSSI-50, CFB in Total PSD score at Week 8, CFB in Total PSD score at Week 4, and PSSI-90 at Week 8. The remaining  $\alpha = 0.02$  will be used to test the second family, comprised of the Scalp WI-NRS at Week 8, the Scalp WI-NRS at Week 4, and the Scalp WI-NRS at Week 2. The tests within this second family will be hierarchical, beginning with the endpoint at Week 8, followed by Week 4 and Week 2. .

**Figure 3: Primary and Secondary Endpoint Testing**

Achievement of IGA success is a score of 'clear' or 'almost clear' plus a 2 grade improvement from baseline.  
Scalp WI-NRS success is a 4 point reduction in WI-NRS among subjects with WI-NRS  $\geq 4$  at baseline.  
CFB – Change from baseline

The binary secondary endpoints will be analyzed using a Cochran-Mantel-Haenszel test stratified by country, baseline S-IGA, and baseline B-IGA similar to the primary endpoint.

The continuous secondary endpoints will be analyzed using an analysis of covariance with treatment, the stratification factors including country, baseline S-IGA, and baseline B-IGA, and baseline value as independent variables. Statistical comparison between the active treatment arm and vehicle arm will be facilitated by using contrasts.

Time-to-event endpoints will be analyzed using the Kaplan-Meier estimator. Treatment group comparisons will be performed using the log-rank statistic.

Sensitivity analyses of secondary endpoints may be conducted in by study site or groups of study sites.

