	
subjects for binary endpoints/categorical data, and mean, SD, median, minimum, and maximum for continuous data.
 
The primary endpoint of ‘S-IGA success at Week 8’ will be analyzed using a Cochran-Mantel-Haenszel test stratified by country, baseline S-IGA (2 vs. <math>\geq 3</math>), and baseline B-IGA (2 vs. <math>\geq 3</math>). The analysis will be performed on the Intention-to-Treat (ITT) population and missing data will be imputed using multiple imputation.
 
Continuous secondary and exploratory endpoints will be analyzed using Analysis of Covariance with treatment and stratification factors as independent variables. The ITT population will be used, and missing data will be imputed using multiple imputation. Binary secondary and exploratory endpoints will be analyzed similarly to the primary endpoint. Time-to-event endpoints will be analyzed using the Kaplan-Meier estimator. Treatment group comparisons will be performed using the log-rank statistic. To control for multiple comparisons among the secondary endpoints, the following testing plan will be used:
 
Upon demonstration of statistical significance for S-IGA Success at Week 8, the secondary endpoint of B-IGA Success at Week 8 will be tested hierarchically at the 5% significance level. If the test for B-IGA Success at Week 8 is significant, the <math>\alpha</math> of 0.05 will be split to test 2 families of secondary endpoints. The first family will be comprised of the PSSI-75, which will be tested at <math>\alpha = 0.03</math> level. If the test of PSSI-75 is statistically significant, the <math>\alpha=0.03</math> will be used with a Holm testing procedure to test the 4-endpoints of time to success in PSSI-50, CFB in Total PSD score at Week 8, CFB in Total PSD score at Week 4, and PSSI-90 at Week 8. The remaining <math>\alpha = 0.02</math> will be used to test the second family, comprised of the Scalp WI-NRS at Week 8, the Scalp WI-NRS at Week 4, and the Scalp WI-NRS at Week 2. The tests within this second family will be hierarchical, beginning with the endpoint at Week 8, followed by Week 4 and Week 2.

--	---

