6.1.3. Multiple Comparisons

To control for multiple comparisons among the secondary endpoints, the following testing plan will be used, as outlined in Figure 1.

Upon demonstration of statistical significance for S-IGA Success at Week 8, the secondary endpoint of B-IGA Success at Week 8 will be tested hierarchically at the 5% significance level.

If the test for B-IGA Success at Week 8 is significant, the α of 0.05 will be split to test 2 families of secondary endpoints. The first family comprise the PSSI-75, which will be tested at the $\alpha = 0.03$ level. If the test of PSSI-75 is statistically significant, then $\alpha = 0.03$ will be used with a Holm testing procedure to test the 4 endpoints of time to success in PSSI-50, change from baseline in Total PSD score at Week 8, change from baseline in Total PSD score at Week 4, and PSSI-90 at Week 8. The remaining $\alpha = 0.02$ will be used to test the second family, comprising the SI-NRS at Week 8, the SI-NRS at Week 4, and the SI-NRS at Week 2. The tests within this second family will be hierarchical, beginning with the endpoint at Week 8, followed by Week 4 and Week 2.

Figure 1: Primary and Secondary Endpoint Testing

Achievement of IGA success is a score of “clear” or “almost clear” plus a 2-grade improvement from baseline.
 SI-WRS Success is a 4-point reduction in SI-NRS among subjects with SI-NRS ≥ 4 at baseline.
 B-IGA = Body-Investigator Global Assessment; EP = endpoint; CFB = change from baseline; PSSI = Psoriasis Scalp Severity Index; S-IGA = Scalp-Investigator Global Assessment; SI-NRS = Scalp Itch - Numeric Rating Scale.

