datasets, depending on the number of imputed monotone datasets that are required. The seed may be changed after unblinding in case of any issues with the imputation process, and it will be documented in the CSR if any change is required.

3. For each completed dataset, compute the necessary derived variables. The dichotomous success rate (clear or almost clear with at least a 2-point change from baseline) will be derived. The results obtained will be analyzed using the Cochran-Mantel-Haenszel (CMH) analysis for each of the complete analysis data sets stratified by baseline S-IGA score category, baseline B-IGA score category, and country. The results will be combined into one multiple imputation inference (odds ratio, associated CI, and *P* value) using PROC MIANALYZE as illustrated⁴.

This approach to imputation should be superior to other strategies such as carrying forward the last available observation, which may yield unrealistic imputed values. Also, the use of multiple imputation avoids the problem of artificially increasing power through data imputation associated with single-imputation methods because it accounts for the uncertainty associated with the imputation. Other missing data will not be imputed, with the exception of incomplete dates as described in Section 6.1.8. For responder analyses, missing data will be treated as a nonresponse with the exception of S-IGA. Only observed data will be summarized using descriptive statistics.

The SAS pseudo code for the multiple imputation process is listed below:

Step 1:

```
proc mi data=example seed=34978264 nimpute=XX round=1 out=example_1;  
  mcmc impute=monotone;  
  var <baseline score> ..... <visit8 score>;  
run;
```

Step 2:

```
proc mi data=example_1 seed=51192215 nimpute=XX out=example_2;  
  class <treatment> <country>;  
  monotone regpmm(<baseline score> ..... <visit8 score>);  
  var <treatment> <country> <baseline score> ..... <visit8 score>;  
run;
```

XX will be determined based on the proportion of missing data across visits.

Step 3: This step involves running CMH test stratified by baseline S-IGA score category, baseline B-IGA score category, and country on each completed dataset and combining the results using PROC MIANALYZE.

```
proc freq data=example noprint;  
  by <imputationnumber> <visit> ;  
  tables <country> * <BL S-IGA cat> * <BL B-IGA cat> * <treatment> *  
    <outcome> / cmh alpha=0.05;  
  output out=example_stat cmh;  
run;
```

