- **CDLQI Score** = sum of the 10 questions (individual questions scored as Very much=3, Quite a lot=2, Only a little=1, Not at all=0; Question 7: if the last week was school time, the question was scored as Very much=3, Quite a lot=2, Only a little=1, Not at all=0, with Prevented school recoded to 3, and if the last week was vacation, the standard responses apply; range for score 0 to 30). If 1 item is missing, that item is scored as 0. If 2 or more items are missing, the score should not be calculated.

- **PSD Total score** = sum of the 16 questions (individual questions scored 0 to 10, where higher scores indicate more severe symptoms; range for total score 0 to 160). If 1 or more items are missing, the score is not calculated.
- **Compliance** = number of applications divided by the expected number of IP applications for each subject. Compliance will be calculated using drug accountability data over the entire treatment period for each subject, up to treatment completion or discontinuation.
 - **Number of expected IP applications** = 56 for subjects who complete the study or number of days between first and last application of IP (last treatment date - first treatment date + 1) for subjects who discontinue early from the study.
 - **Number of IP applications** = number of expected IP applications – missed IP applications as collected in the electronic case report form (eCRF).
- **Weight of IP (g)** = returned can weight – dispensed can weight.
- **Body mass index (BMI) (kg/m²)** = [weight (kg) / height (cm) / height (cm)] x 10,000.
- **BMI Categories**
 - Underweight: BMI < 18.5
 - Normal: 18.5 ≤ BMI ≤ 24.9
 - Overweight: 25.0 ≤ BMI ≤ 29.9
 - Obese: BMI ≥ 30.0
- **Change from baseline** = value at current time point – value at baseline.
- **Treatment emergent AE (TEAE)** = any AE with an onset date/time after the first application of IP.
- **PHQ-8** = sum of the 8 questions (individual questions scored as Not at all=0, Several days=1, More than half the days=2, and Nearly every day=3; range for score 0 to 24). If more than 1 item is missing, the score should not be calculated. If 1 item is missing, the score is calculated as (sum of answered items*8)/number of answered items.

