Sensitivity analyses of the primary endpoint will also be performed using the original (nonimputed) dataset. These will include a repeated measures logistic regression model (GEE) with S-IGA success as the dependent variable and treatment, country, visit, and baseline S-IGA score as the independent variables.

Achievement of a score of clear will also be analyzed using the CMH test, on nonimputed data.

A tipping point analysis will be performed as described in Section 6.1.4.2. For the tipping point analysis, a figure will be provided that displays the P values in the analysis plotted against the range of shift parameters; included in this figure will be the shift parameters and P values for the range of shift parameters to provide information on where the analysis tips from significant to non-significant.

Subgroup Analyses – Observed Data

For the primary endpoint of IGA success (S-IGA of “Clear” or “Almost Clear” plus a 2-grade improvement from baseline at Week 8), the CMH analysis will be performed on the following subgroups, using observed data:

- Topical Corticosteroids – Naïve Subjects
- Topical Vitamin D Derivatives – Naïve Subjects
- Psoriasis involvement on the knee and/or elbow
- Subjects who achieved both S-IGA and B-IGA success at Week 8
- By Study Site

Subgroup Analyses – Multiple Imputation Data

For the primary endpoint of IGA success (S-IGA of “Clear” or “Almost Clear” plus a 2-grade improvement from baseline at Week 8), the CMH analysis will be performed on the following subgroups, using multiple imputation data:

- Baseline S-IGA = 3
- Baseline S-IGA = 4
- Age Category = 12-17 years
- Age Category = ≥ 18 years
- Subjects who achieved both S-IGA and B-IGA success at Week 8

Continuous Data Analysis

Analysis of change from baseline in S-IGA scores at Weeks 2, 4, 8, and 9 will be performed using descriptive summaries (mean, median, inter-quartile range) by treatment group and study visit. These descriptive statistics will also be presented based on the multiple imputation data.

All Analyses

All other missing data for all other analyses and summaries will remain missing and will not be imputed. All weeks will be included in these analyses, although only Week 8 using the ITT population will be included in the testing strategy.

The primary efficacy analysis will be based on ITT population, and all of the above analyses will be repeated for the mITT population.

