8.2.4. Psoriasis Symptoms Diary (PSD)

The PSD assesses the severity of symptoms or how bothersome are the symptoms of psoriasis. The PSD will be analyzed as follows:

- Change and percent change from baseline to Weeks 2, 4, and 8 in the PSD individual item and total scores will be analyzed using descriptive statistics and an ANCOVA (total score only) with terms for country, baseline S-IGA category, and baseline B-IGA category, and baseline PSD score as a covariate. Statistical comparisons between the treatment groups will be obtained using contrasts. The LS means, standard errors, 95% CIs, and *P* values will be presented. Only change from baseline in PSD total score at Weeks 4 and 8 using the ITT population will be included in the testing strategy.

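### The SAP drops the multiple imputation that the protocol synopsis specifies for PSD change, so the two alpha-controlled PSD tests ignore earlier PSD scores and can understate the effect if post-baseline dropout differs by arm

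*Protocol*

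**What the plan says.** **Protocol.** Section 6.3.2 names the model: "The continuous secondary endpoints will be analyzed using an analysis of covariance with treatment, the stratification factors including country, baseline S-IGA, and baseline B-IGA", together with the baseline value. It gives no missing-data rule. The synopsis (1.1, Statistical Considerations) gives one for the continuous secondary endpoints: "The ITT population will be used, and missing data will be imputed using multiple imputation".

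**SAP.** Section 6.1.4.1 confines multiple imputation to S-IGA and then states: "Other missing data will not be imputed, with the exception of incomplete dates as described in Section 6.1.8". Section 8.1.1 repeats it: "All other missing data for all other analyses and summaries will remain missing and will not be imputed". Section 8.2.4 analyses PSD total change at Weeks 2, 4 and 8 by ANCOVA, with country, the two baseline IGA categories and baseline PSD in the model. It adds: "Only change from baseline in PSD total score at Weeks 4 and 8 using the ITT population will be included in the testing strategy". No post-baseline PSD score enters the model for a later visit.

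**Place in the testing plan.** SAP 6.1.3 says that alpha of 0.03 "will be used with a Holm testing procedure to test the 4 endpoints"; PSD change at Week 8 and at Week 4 are two of those four.

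**How a PSD total goes missing.** PSD is collected at Screening, Baseline and Weeks 2, 4 and 8, in adults only (Protocol 5.2.7). An early termination visit follows the Week 9 procedures (Protocol 5.5), and Week 9 has no PSD (Protocol 1.3). For the 16-item total, SAP 6.1.7 says: "If 1 or more items are missing, the score is not calculated".

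**The concern.** The two documents prescribe different handling of missing data for the same two alpha-controlled endpoints. SAP section 10 lists other departures from the protocol, but not this one.

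Under the SAP rule, a subject with PSD at Weeks 2 and 4 but no Week 8 total contributes nothing to the Week 8 test, although the earlier scores say much about where that subject was heading. Someone who leaves early will normally have no PSD at the termination visit, so the visit windows in SAP 6.1.5 cannot recover a score.

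In a vehicle-controlled trial it is plausible that non-improvers leave more often on vehicle, and SAP 8.1.1 itself names lack of effect as a possible reason for stopping treatment. The vehicle subjects who remain would then look better than the group that was randomised, and a real benefit would be understated. Nothing planned would reveal this. The tipping point analysis (SAP 6.1.4.2) covers S-IGA only, and the mITT repeat removes subjects without filling in any score.

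**Working it through.** **1. Passages side by side.** The synopsis prescribes ANCOVA on ITT with multiple imputation for continuous secondary endpoints. SAP 6.1.4.1, 8.1.1 and 8.2.4 together give ANCOVA at each visit without imputation. The nonresponse rule in 6.1.4.1 is for responder analyses and does not reach a continuous score. Section 10 is silent. This contradiction rests on no assumption.

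**2. Inputs for the size.** The documents give no PSD standard deviation, effect, between-visit correlation or dropout rate. Protocol 6.1.1 says only that power suffices for most secondary endpoints, so there is no PSD figure to reproduce.
- From the documents: about 200 versus 100 subjects; Holm over four endpoints at 0.03, so the first step is 0.03/4 = 0.0075.
- Assumed: residual SD 32; Week 4 to Week 8 residual correlation 0.75; true differences −12 at Week 8 and −9 at Week 4; probability of a missing Week 8 score logistic in the standardised Week 4 change (slope 1.0 or 1.5), calibrated to each arm's missing rate.

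**3. Complete-data benchmark.** SE = 32 × √(1/200 + 1/100) = 3.92, and 12/3.92 = 3.06. The two-sided critical value at 0.0075 is 2.67. Power ≈ Φ(3.06 − 2.67) = Φ(0.39) ≈ 65%.

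**4. Simulated Week 8 estimate (true −12).**

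| Missing, active / vehicle | Observed-data ANCOVA | Shortfall |
|---|---|---|
| 10% / 10% | no material bias | about 0 |
| 20% / 20% | about −12 | about 0 |
| 10% / 12% | about −11.5 | 4% |
| 10% / 15% | −10.7 to −11.0 | 8–11% |
| 10% / 20% | −9.4 to −10.0 | 17–22% |

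Shortfall is (12 − |estimate|)/12; for example (12 − 10.0)/12 = 17%. A likelihood estimate using the Week 4 scores stays near −12 throughout.

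**5. Power at 0.0075 with 10% / 20% missing.** Simulation gives about 34–39% for the observed-data ANCOVA and 59–60% for the likelihood model using Week 4. A hand check agrees. With 180 and 80 subjects left, SE = 32 × √(1/180 + 1/80) = 4.30.
- No bias: 12/4.30 = 2.79; Φ(2.79 − 2.67) ≈ 55%.
- Estimate −10.0: 10.0/4.30 = 2.33; Φ(2.33 − 2.67) ≈ 36%.
- Estimate −9.4: 9.4/4.30 = 2.19; Φ(2.19 − 2.67) ≈ 31%.

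So about 10 points of the fall from 65% come from lost subjects, and most of the rest comes from bias. Simulated power is slightly above the hand figures because selective loss narrows the spread of the remaining scores.

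**6. When bias is small.** A separate simulation in SD units (correlation 0.5 or 0.7, 10–20% dropout, true effect 0.5 SD) gave Week 8 bias within 0.01 SD when dropout was random or depended on baseline only, and 0.01–0.02 SD when it depended on Week 2 and 4 scores alike in both arms. Bias was 0.03–0.05 SD when only vehicle dropout depended on those scores, and 0.05–0.10 SD when the dependence ran in opposite directions by arm. Week 4 bias was about half of each.

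**The case against.** Several points on the other side stand.

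- **Most forms of dropout do little harm.** A reader might infer that any dependence of dropout on symptoms biases the result. It does not: baseline PSD is a covariate, and equal dependence in both arms leaves the difference almost unchanged. The difference between arms is essential, and the documents give no rate from which to predict one.
- **Type I error.** A reader might infer that the observed-data test makes a false efficacy claim more likely. The check does not support that for the dropout pattern of concern. With no effect, 10% versus 25% missing and a nominal two-sided 3%, total rejections rise to about 7.0–8.7%, but 6.8–8.5 points favour vehicle and only about 0.2 favour active, against a nominal 1.5. The harm is an understated effect and lost power.
- **The protocol section is not at fault.** Protocol 6.3.2 might be read as planning an observed-data test. It is silent on missing data, and the synopsis prescribes imputation. The defect is in the SAP.
- **The PSD set is smaller.** Only adults complete the PSD while the trial enrols from age 12, so 200 versus 100 overstates its size and the power figures are somewhat high for both methods.
- **A safeguard exists.** SAP 6.2 allows remote PSD collection during COVID-19 disruption. That limits missingness from closed sites, but not from subjects who leave because they do not improve.

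None of this removes the contradiction or the discarding of usable scores.

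**Conclusion.** The point holds in this form. The SAP replaces the synopsis's multiple imputation with observed-data, single-visit ANCOVA for two alpha-controlled endpoints and does not declare the change. That part is certain.

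The consequence is conditional. If missing Week 8 totals depend on post-baseline symptoms and are more frequent on vehicle, the effect is understated: by roughly a tenth at 10% versus 15% missing and by about a fifth at 10% versus 20%, where power at the first Holm step falls to a little over half of what the existing data could give. These sizes rest on the assumed SD, correlation, effects and dropout model, and are illustrations only. Week 4 bias is smaller. With dropout that depends on baseline alone, or alike in both arms, there is little to correct.

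**What to change.** In SAP 6.1.4.1, 8.1.1 and 8.2.4 (Tables 14.2.5.3 and 14.2.5.4), restore agreement with the synopsis. Impute missing PSD totals by multiple imputation with baseline, Week 2 and Week 4 PSD, treatment and the stratification factors in the model, then run the planned ANCOVA and combine the results. An equivalent option is one repeated-measures model on PSD change at Weeks 2, 4 and 8, with the Week 8 and Week 4 treatment contrasts taken from it and a fallback order for the covariance structure stated in advance.

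Carry those results into the Holm step and keep the observed-data ANCOVA as a sensitivity analysis. List any remaining departure from the protocol in SAP section 10, with its reason.

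The cost is SAP wording and modest programming; no new data are needed. Both methods still assume that data are missing at random, so neither protects against dropout driven by unobserved Week 8 symptoms.
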